1.3.2 Potential Benefits

All study participants will be given the opportunity to receive “enhanced” EPI vaccination. There should be improved protection against measles with the receipt of two doses of a measles-containing vaccine. The receipt of this vaccine, containing rubella, also benefits the infant through protection from rubella. Instead of the monovalent meningitis vaccine (MenAfriVac), participants will receive either the pentavalent NmCV-5 vaccine or the quadrivalent MenACWY-TT vaccine. There is the possible benefit of being afforded protection against some of the additional meningococcal serogroups which are known to cause invasive disease in sub-Saharan Africa. All study participants will have close monitoring with scheduled follow-up visits with the research clinic and this close follow-up may also provide a benefit to the infant through improved access to medical care.

2 STUDY DESIGN, OBJECTIVES AND ENDPOINTS OR OUTCOME MEASURES

2.1 Study Design Description

Infants aged 9 months (eligibility 9-11 months) will be consented, enrolled at Step 1, and randomized. A first-step randomization at a 1:1.2 ratio will determine whether the infant will receive blinded meningococcal study product at the 9-month (Group 1, n=600) or the 15-month (Group 2, n=720) enhanced EPI vaccination visit. Within the 9-month or 15-month age groups, a second-step randomization at a 2:1 ratio will determine whether the study participant will receive a single dose of NmCV-5 (Group 1A or 2A) or a single dose of control vaccine, MenACWY-TT (Group 1B or 2B). The infant will be considered enrolled upon the successful first step randomization of the study, which will occur at the time of presenting to their 9-month EPI visit.

If the randomized study product is to be administered at the 15-month visit, the prospectively identified and consented infants will complete their designated “enhanced” EPI immunizations at the 9-month visit, except no meningococcal vaccine will be administered. At their 15-month visit (eligibility 15-17 months), these infants will receive a single dose of NmCV-5 or a single dose of control vaccine, as per the second-step randomization at a 2:1 ratio. Because we anticipate up to 20% of infants may be lost to follow-up (i.e., fail to return to the clinic for their 15-month visit) or may become ineligible (e.g., receives MenAfriVac prior to the 15-month visit), there is the plan to over randomize study infants into the 15-month group—this is the underlying reason for the first-step randomization at 1:1.2. Upon successful randomization of 600 eligible infants into the 15-month groups, all remaining prospectively identified infants (up to n=120) regardless of age upon return will be offered immunization with MenACWY-TT and the “enhanced” EPI vaccinations from available study supply, but otherwise are no longer eligible for the study (i.e., will not be followed in the context of this study). If “enhanced” EPI vaccinations are declined or not available, infants will be referred to local clinic for standard EPI vaccination.

In this study, “enhanced” EPI vaccines will be co-administered at indicated time points. There will be a measles and rubella-containing vaccine (i.e., MR) and yellow fever vaccine at 9-months and a second dose of a measles and rubella-containing vaccine at 15-months. Concurrent administration of these EPI vaccines with the blinded study product (i.e., co-administration of these vaccines in the same visit) is acceptable and preferred. Study blood samples are to be obtained at four timepoints for all study infants; at baseline prior to meningococcal vaccination, at 28-days, 6-months and 2 years after meningococcal vaccination. The study is designed to have at least 90% power to meet both the primary non-inferiority objective compared to MenACWY-TT and the objectives related to non-interference with co-administered vaccines.

Table 5: Study Group Design

Group	9 (9) months of age	15 ¹ (15) months of age	Primary endpoint measurement	Immuno- persistence
1A (n=400)	NmCV-5 + MR + YF	MR	Serology 28-days post-vaccination	Serology 6- months and 2- years post-vaccination
1B (n=200)	MenACWY-TT + MR + YF	MR		
2A (n=400)	MR + YF	NmCV-5 + MR		
2B (n=200)	MR + YF	MenACWY-TT +MR		
NmCV-5 = pentavalent meningococcal conjugate vaccine; MenACWY-TT = quadrivalent meningococcal conjugate vaccine; MR = measles-rubella containing vaccine; YF = yellow fever vaccine; ¹ Once 600 children are randomized to Groups 2A and 2B, the remaining prospectively identified infants (up to n=120) will be provided immunization with MenACWY-TT + MR and will not complete follow up study visits.				

Because the study vaccines may have different appearances, it may not be possible for the vaccinator to be blinded. Designated vaccinators will not partake in any post-vaccination evaluation. Parents or guardians of participants, laboratory personnel, and the researchers responsible for evaluation will remain blinded. Study vaccinations will be administered in a monitored environment where treatment for immediate reactions such as anaphylaxis, will be available. Study physicians will be onsite during all vaccinations, and subjects will be observed for 30 minutes following vaccination. The rabbit complement-dependent serum bactericidal antibody (rSBA) assay will be performed at UK Health Security Agency (UKHSA) in Manchester, UK, an international reference laboratory for meningococcal vaccine immunology. UKHSA performed the assays for all trials of MenAfriVac as well as the Phase I and II trials of NmCV-5. Immunological assays for measles, rubella, and yellow fever will be performed at VisMederi in Siena, Italy. .

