4.2.2 Subject Replacement

Subjects who withdraw, or are withdrawn from this study, or are lost to follow-up after signing the informed consent form (ICF) and either before or after administration of the study product will not be replaced.

4.2.3 Participants who are randomized into Group 2 (15-month) but are not vaccinated with a randomized meningococcal vaccine

Subjects that are randomized to Group 2 (with Step 1 randomization) and present to the 15-month of age visit that do not have second-step randomization because the target enrollment sample size has been fulfilled will be offered “enhanced” EPI vaccination (i.e., MR vaccine and MenACWY-TT vaccine in open-label fashion) but will not receive further scheduled follow-up visits in the study.

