5.2 Enrollment

At Visit Day 1, upon confirmation of ongoing informed consent and the eligibility of the subject, there will be a second step randomization (Step 2 Randomization) at a 2:1 ratio to determine whether the infant will receive experimental vaccine or active control vaccine, as a blinded study product. This second step randomization will occur on the day subjects are to receive their first study injection (at 9 or 15 months of age based on Step 1 Randomization), after confirmation of eligibility and immediately prior to injection.

The unblinded designated personnel will be provided with the randomization list that includes treatment assignment. Based on the assigned treatment the unblinded personnel will prepare the study vaccine to be given to each subject. The unblinded personnel will maintain the randomization list in a secure place.

If for any reason, after signing the informed consent form, the subject (who has passed screening) fails to be randomized, the reason for not being randomized should be recorded in source documents and eCRFs. For the 15-month groups, if the target Step 2 randomized sample size of 600 has been achieved, then the study will be closed to further second step randomizations. Study participants that are unable to receive meningococcal study product with step 2 randomization, due to closure to further enrollments, will be provided quadrivalent meningococcal conjugate vaccine (open-label) and will not be required to have further study follow up.

Visit #1 (Day 1 for Group 1)

- Confirm informed consent
- Review for any changes to the medical history (if not same day as screening), including review of systems.
 - Review of systems: an interview that queries the subject's parent/guardian as to any clinical findings the subject has experienced across each organ system (if not

same day as screening). The questions tend to be grouped by system organ class and are intended to remind the parent/guardian of any forgotten or medical conditions that may be relevant.

- Review of prior/concomitant medications and prior vaccinations (if not same day as screening)

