9.3 Sample Size Considerations

Table 8 shows power to test the non-inferiority of the seroprotective response to each of the serogroups A, C, W and Y elicited by the NmCV-5 vaccine, relative to the seroprotective response elicited by the MenACWY-TT vaccine, when administered as a single dose at either 9 months of age or 15 months of age. These calculations assume a non-inferiority margin of -10% (-0.1) for a one-sided hypothesis test, with a 2.5% Type I error rate, and using the Miettinen-Nurminen method for estimation of the 95% CI for the difference in proportions. The resulting power correspond to the sample size of at least 183 and 366 evaluable participants in each of the MenACWY-TT and NmCV-5 arms, respectively, where this target sample size results from the following assumptions:

- At least 600 enrolled participants will be randomly assigned to receive the study vaccine at 9 months of age and
- Among those randomized to receive the study vaccine at 15 months of age, at least 600 participants will receive it at the scheduled visit.
- For each vaccination age, participants will be randomly assigned, in a 1:2 ratio, to receive the MenACWY-TT or the NmCV-5 vaccine.

- At least 92.5% of the 600 enrolled and vaccinated participants will be followed up and contribute a sample for assessment at their Day 29 visit.

Finally, calculation of Power in Table 8 is based on assumed proportions of seroprotective response in the MenACWY-TT arms that are consistent with, if somewhat more conservative than, to those reported in the literature.

Table 8. Power to test non-inferiority of the proportion of participant with seroprotective response at Day 29 for serogroup A, C, W and Y, for a non-inferiority margin of -10% (-0.1) and a sample size of at least 183 and 366 evaluable participants in MenACWY-TT and NmCV-5 arms, respectively.

Serogroup	Proportion of Sero-response in MenACWY-TT arm	Difference in proportion of sero-response (NmCV-5 – MenACWY-TT)		Power
		Under the Null (H0)	Under the Alternative (H1)	
A	0.95	-0.1	0	99.97%
C	0.95	-0.1	0	99.97%
W	0.90	-0.1	0	97.50%
Y	0.90	-0.1	0	97.50%

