Power calculations were performed computationally, based on the exact distribution of the primary endpoint of interest under the alternative hypothesis. The probability of each combination of outcomes in the active and control arms was obtained under the assumption that they follow independent binomial distributions. The power of the test was calculated as the sum of probabilities of those scenarios where the outcomes meet the non-inferiority criterion. A simulation was also conducted to corroborate the results.

Table 9 shows power to test the non-inferiority of the seroprotective response to serogroup X. Unlike serogroups A, C, W and Y, non-inferiority of the vaccine for serogroup X will be based on the difference in the proportion of participants randomized to receive NmCV-5 with seroprotective response to serogroup X minus the proportion of participants randomized to receive MenACWY-TT with seroprotective response to the serogroup with the lowest proportion of seroprotective response. Thus, for this test, and consistent with our assumptions listed above, we assume that the lowest proportion of seroprotective response in the MenACWY-TT will be 90% or higher.

Table 9. Power to test non-inferiority of the proportion of participant with seroprotective response at Day 29 for serogroup X, when compared to lowest seroprotective response rate among A, C, W, Y serogroups, with a non-inferiority margin of -10% (-0.1) and a sample size of at least 183 and 366 evaluable participants in MenACWY-TT and NmCV-5 arms, respectively.

Serogroup	Lowest Proportion of Sero-response among Serogroups A, C, W,	Difference in sero-response (Serogroup X in NmCV-5 - lowest proportion among Serogroups A, C, W, Y in MenACWY-TT)	Power
-----------	--	---	-------

	Y in MenACWY-TT arm	Under the Null (H0)	Under the Alternative (H1)	
X	0.90	-0.1	0	97.50%

Under the assumption that the test statistics used for the five non-inferiority tests described above are independent, the power to declare overall non-inferiority of NmCV-5 relative to MenACWY-TT at a given vaccination age is calculated to be at least 92.6%. We note, however, that this is a conservative assumption and, given the likely correlation between seroprotective response rates among all the serogroups, the overall power may be higher.

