### 2.2 General Design Considerations

Infants aged 9 months (eligibility 9-11 months) will be consented, enrolled at Step 1, and randomized. A first-step randomization at a 1:1.2 ratio will determine whether the infant will receive blinded meningococcal study product at the 9-month (Group 1, n=600) or the 15-month (Group 2, n=720) enhanced EPI vaccination visit. Within the 9-month or 15-month age groups, a second-step randomization at a 2:1 ratio will determine whether the study participant will receive a single dose of NmCV-5 (Group 1A or 2A) or a single dose of control vaccine, MenACWY-TT (Group 1B or 2B). The infant will be considered enrolled upon the successful first step randomization of the study, which will occur at the time of presenting to their 9-month EPI visit.

If the randomized study product is to be administered at the 15-month visit, the prospectively identified and consented infants will complete their designated “enhanced” EPI immunizations at the 9-month visit, except no meningococcal vaccine will be administered. At their 15-month visit (eligibility 15-17 months), these infants will receive a single dose of NmCV-5 or a single dose of control vaccine, as per the second-step randomization at a 2:1 ratio. Because we anticipate up to 20% of infants may be lost to follow-up (i.e., fail to return to the clinic for their 15-month visit) or may become ineligible (e.g., receives MenAfriVac prior to the 15-month visit), there is the plan to over randomize study infants into the 15-month group—this is the underlying reason for the first-step randomization at 1:1.2. Upon successful randomization of 600 eligible infants into the 15-month groups, all remaining prospectively identified infants (up to n=120) regardless of age upon return will be offered immunization with MenACWY-TT and the “enhanced” EPI vaccinations from available study supply, but otherwise are no longer eligible for the study (i.e., will not be followed in the context of this study)

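### The 1:1.2 Step 1 ratio (720 for 600) is justified by a loss of up to 20%, but it covers a loss of at most 16.7%

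*Protocol*

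**What the plan says.** Protocol 2.1 randomizes infants at Step 1 in a 1:1.2 ratio, 600 to Group 1 (9 months) and 720 to Group 2 (15 months). The reason given is "Because we anticipate up to 20% of infants may be lost to follow-up" or become ineligible before the 15-month visit. SAP 2.2 repeats this and states that "this is the underlying reason for the first-step randomization at 1:1.2".

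Two rules fix what can happen to the Group 2 number after that. Under Protocol 4.2.2, infants who withdraw or are lost "either before or after administration of the study product will not be replaced". Under Protocol 5.2, "if the target Step 2 randomized sample size of 600 has been achieved, then the study will be closed to further second step randomizations".

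Protocol 9.3 and SAP 2.6 then build the power calculation on these assumptions:

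- "Among those randomized to receive the study vaccine at 15 months of age, at least 600 participants will receive it at the scheduled visit".
- "At least 92.5% of the 600 enrolled and vaccinated participants will be followed up and contribute a sample" at Day 29.
- Step 2 allocation is 1:2, giving at least 183 MenACWY-TT and 366 NmCV-5 evaluable infants per age group.

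From these, overall power "at a given vaccination age is calculated to be at least 92.6"%. Protocol 2.1 sets the design target: "The study is designed to have at least 90% power to meet both the primary non-inferiority objective".

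**The concern.** Allowing for a loss fraction *d* means dividing the required number by (1 − *d*). The figure of 720 comes from multiplying by (1 + *d*), which falls short whenever *d* is above zero. The 1:1.2 ratio therefore does not cover the loss that is given as its reason.

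Nothing else in the plan closes the gap. There is no replacement, and Step 2 closes at 600, so 600 is a ceiling as well as the assumed minimum. For Group 2, the assumption of at least 600 vaccinated can be met only exactly, and only if loss stays at or below 16.7%.

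At stake are the sample size and power quoted for one of the two co-primary objectives, which has its own report to WHO (SAP 3.1). If loss falls between 16.7% and 20%, Group 2 misses its stated size even though loss stayed within the range the plan says it allowed for.

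**Working it through.** **Inputs.** Target vaccinated 600; Step 1 Group 2 size 720; anticipated loss up to 20% (Protocol 2.1, SAP 2.2). Step 2 allocation 2:1; 92.5% sampled at Day 29; 366/183 evaluable; margin −10%; one-sided 2.5%; Miettinen-Nurminen limits; comparator rates 0.95 (A, C) and 0.90 (W, Y and the comparator for X); true difference 0 (Protocol 9.3, SAP 2.6).

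**Where 720 comes from.** 600 × (1 + 0.20) = 720. Allowing for a 20% loss gives 600/(1 − 0.20) = 750, a ratio of 1:1.25.

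**What 720 covers.**

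- Largest loss that still leaves 600: 1 − 600/720 = 16.7%.
- At 20% loss: 720 × 0.80 = 576 vaccinated (384/192), which is 24 short.
- Evaluable at 20% loss: 576 × 0.925 = 532.8, about 355/178, which is 11 and 5 short of 366/183.
- Loss at which 366/183 is first missed: 549/0.925 = 593.5 vaccinated, and 1 − 593.5/720 = 17.6%.
- If each infant is lost independently with probability 20% (an assumption), the chance that at least 600 of 720 return is about 1.3%.

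**Power by the plan's method.** Exact binomial enumeration, counting a success when the Miettinen-Nurminen lower limit is above −0.10. Overall power = (power at 0.95)² × (power at 0.90)³. The 366/183 row reproduces the plan's 99.97%, 97.50% and 92.6%.

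| Loss before 15 months | Evaluable | Power at 0.95 | Power at 0.90 | Overall |
|---|---|---|---|---|
| up to 16.7% | 370/185 | 99.97% | 97.61% | 93.0% |
| 17.6% | 366/183 | 99.97% | 97.50% | 92.6% |
| 19% | 360/180 | 99.97% | 97.28% | 92.0% |
| 20% | 355/178 | 99.96% | 97.09% | 91.4% |
| 23.3% | 341/170 | 99.94% | 96.61% | 90.1% |
| 23.4% | 340/170 | 99.94% | 96.43% | 89.6% |

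**Serogroup X under the SAP.** The planning method treats the comparator for X as a single rate of 0.90. SAP 8.2.2 instead uses a bootstrap interval for the difference from the lowest observed rate among A, C, W and Y. Simulating that rule at the plan's rates with independent serogroups (6000 trials, 1000 resamples) gave X power of about 99.9% at 355/178. The exact product for A, C, W and Y alone is 0.9996² × 0.9709² = 94.2%, so overall power under the SAP rule is about 0.942 × 0.999 = 94.1%. The direct simulation gave 93.7%, with a standard error of about 0.3 points. At 366/183 it gave 95.3%, slightly above the exact four-serogroup ceiling of 0.9997² × 0.9750² = 95.0%. Simulation differences of this size are noise and should not be read as the cost of the shortfall.

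**A smaller mismatch in the same list.** 92.5% of 600 is 555, or 370/185. The stated 366/183 totals 549, which is 91.5% of 600. This errs on the conservative side.

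**The case against.** The strongest reply is that 20% is a ceiling. At 16.7% loss or less the plan delivers its 600, and the evaluable target survives to about 17.6%, so the shortfall exists only in the top 3.3 points of the range for vaccinated infants and the top 2.4 points for evaluable ones. The power statement is also conditional: it gives power for at least 366/183 and lists 600 vaccinated as an assumption, without saying that this is reached at 20% loss. Even at 20%, the 90% target is met. Finally, SAP 3.2.3 says 150 Group 1 infants have already been selected for baseline testing. Both groups come from one Step 1 stream, so Step 1 may have been largely complete when the SAP was written, and SAP 6.1 to 6.5 will report the achieved numbers anyway.

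Much of this stands. The consequence is small, no estimate or test changes, and the 92.5%/91.5% mismatch is minor. It does not remove the contradiction, however. The plan names the range up to 20% as the reason for the ratio, and the ratio does not cover the top of that range. The power section then assumes, for that same group, a number that the design cannot deliver there. The point about timing affects which correction is useful: a scenario if Group 2 Step 2 is still open, achieved numbers if it is closed.

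**Conclusion.** The concern holds. The 1:1.2 ratio covers a loss of at most 16.7%. At the 20% the plan anticipates as its upper limit, Group 2 has 576 vaccinated and about 355/178 evaluable, below the stated 600 and 366/183. By the planning method, overall power is about 91.4% against the stated minimum of 92.6%, a loss of about 1.2 points. It falls below the 90% target only from about 23.4% loss.

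These figures rest on the plan's response rates, 92.5% sampling, five independent tests and a fixed 0.90 comparator for X. Under the SAP 8.2.2 rule for X, overall power at 20% loss is about 94%, again with independent serogroups. The defect is a wrong statement of what the over-randomization covers, and it should be corrected. It is not a reason to doubt that the trial is adequately powered.

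**What to change.** 1. **Protocol 2.1 and SAP 2.2.** State that the 1:1.2 ratio (720 for 600) allows for a loss of at most 16.7% before the 15-month visit.
2. **Protocol 9.3 and SAP 2.6.** Add that at 20% loss Group 2 has 576 vaccinated, about 355/178 evaluable at 92.5% sampling, and about 91.4% overall power. Label this figure as the planning approximation, because it is not the power of the SAP 8.2.2 bootstrap test for X. If Group 2 Step 2 randomization is already complete, give the achieved numbers instead.
3. **Minor, in the same edit.** Make the sampling rate and evaluable numbers agree: either 91.5% with 366/183 and 92.6% overall power, or 92.5% with 370/185 and 93.0%.

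The cost is two or three sentences in each document. No extra infants are needed and the analysis does not change.

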2.2 Study Objectives

2.2.1 Primary

- To demonstrate that the immune responses to meningococcal serogroups A, C, Y, W, and X elicited by one dose of NmCV-5 at 9 months of age are non-inferior to the immune responses to meningococcal serogroups A, C, Y, W elicited by one dose of MenACWY-TT at 9 months of age, as measured by rabbit serum bactericidal antibody (rSBA) titers at 28 days after vaccination, and when meningococcal vaccines are given concomitantly with routine vaccines.
- To demonstrate that the immune responses to meningococcal serogroups A, C, Y, W, and X elicited by one dose of NmCV-5 at 15 months of age are non-inferior to the immune responses to meningococcal serogroups A, C, Y, W elicited by one dose of MenACWY-TT at 15 months of age, measured by rSBA titers at 28 days after vaccination, and when meningococcal vaccines are given concomitantly with routine vaccines.

2.2.2 Secondary

- To assess the safety and tolerability of a single dose of NmCV-5 or MenACWY-TT, when given concomitantly with routine vaccines.
- To demonstrate that the immune responses to meningococcal serogroup X elicited by one dose of NmCV-5 (at either 9 or 15 months of age) is superior to that elicited by MenACWY-TT (at either 9 or 15 months of age) measured by rSBA titers at 28 days after vaccination.
- To demonstrate the non-inferiority of immune responses to EPI vaccines (measles-rubella, yellow fever, measles booster) when co-administered with NmCV-5 (at either 9 or 15 months of age) compared to the immune responses when co-administration with MenACWY-TT (at either 9 or 15 months).
- To assess other clinically significant immune response indicators elicited by a single dose of NmCV-5, given concomitantly with routine vaccine, as compared to those elicited by MenACWY-TT.

